**Any Grade 2 ADR should be managed as follows:**

- If a Grade 2 ADR resolves to Grade  $\leq 1$  within 2 weeks treatment may continue
- If a Grade 2 ADR does not resolve to Grade  $\leq 1$  within 2 weeks, bintrafusp alfa should be held. If after another 2 weeks the event has not resolved to Grade 1, the patient should permanently discontinue treatment with bintrafusp alfa (except for hormone insufficiencies, that can be managed by replacement therapy; for these hormone insufficiencies, up to 2 subsequent doses may be omitted)
- Upon the second occurrence of the same Grade 2 ADR (except for hormone insufficiencies that can be managed by replacement therapy) in the same patient, treatment with bintrafusp alfa has to be permanently discontinued

**5.6.4 Management of Infusion Related Reaction (IRR)**

IRRs including hypersensitivity (immediate) were listed as an important identified risk of bintrafusp alfa. IRR are divided into reactions versus signs and symptoms.

- Reactions are considered when onset is on the day of infusion (during or after the infusion) or the day after the infusion (irrespective of resolution date) for infusion related reaction, drug hypersensitivity, anaphylactic reaction, hypersensitivity and Type 1 hypersensitivity
- Signs and symptoms are considered when onset is on the day of infusion (during or after the infusion) and resolved with the end date within 2 days after onset for pyrexia, chills, flushing, hypotension, dyspnea, wheezing, back pain, abdominal pain and urticaria

Pre-medication with an anti-histamine and with paracetamol (acetaminophen) was mandatory in order to mitigate potential infusion related reactions during the first 2 infusions in Study EMR200647-001 and Study MS200647-0008.

**Treatment Modification for Symptoms of Infusion-Related Reactions**

NCI-CTCAE Grade	Treatment Modification
Grade 1 - mild Mild transient reaction; in general, infusion interruption not indicated; intervention not indicated	
 
• Increase monitoring of vital signs as medically indicated as participants are deemed medically stable by the attending Investigator.
 
• Hold infusion if deemed necessary by the investigator.
 

Grade 2 – moderate Therapy or infusion interruption indicated but responds promptly to symptomatic treatment (for example, antihistamines, nonsteroidal anti-inflammatory drugs, narcotics, IV fluids); prophylactic medications indicated for $\leq 24$ h.	
 
• Stop the infusion of the study intervention.
 
• Increase monitoring of vital signs as medically indicated as participants are deemed medically stable by the attending Investigator.
 
• If symptoms resolve quickly, resume infusion at 50% of original rate with close monitoring of any worsening signs and symptoms, otherwise dosing held until resolution of symptoms with mandated premedication for the next scheduled visit.
 
• If not improving, consider administration of glucocorticoids and stop the infusion for that day.
 
• If the participant has a second IRR Grade <math>\geq 2</math> on the slower infusion rate despite premedication, the infusion should be stopped, and the investigator may consider withdrawal of this participant from the study.
 

Grade 3 or Grade 4 – severe or life-threatening 
 
○ Grade 3: Prolonged (for example, not rapidly responsive to symptomatic medication and/or brief interruption of infusion); recurrence of symptoms following initial improvement; hospitalization indicated for clinical sequelae.
 
○ Grade 4: Life-threatening consequences; urgent intervention indicated.
 
	
 
• Stop the infusion of study intervention immediately and disconnect infusion tubing from the participant with additional appropriate medical measures and closely monitor until deemed medically stable by the attending Investigator. Hospitalization and/or close monitoring is recommended
 
• Administration of glucocorticoids may be required
 
• For Grade 3 or 4 IRRs, permanent discontinuation of study intervention is mandated.
 

Once the infusion is interrupted or rate reduced to 50% of previous infusion rate, it must remain decreased for all subsequent infusions. For all types and grades of infusion reactions, details about drug physical constitution, method of preparation, and infusion must be recorded. Participants should be instructed to report any delayed reaction immediately.	
IRR=infusion-related reactions, IV=intravenous, NCI-CTCAE=National Cancer Institute-Common Terminology Criteria for Adverse Event, NSAIDs=nonsteroidal anti-inflammatory drugs.	

#### Immediate Hypersensitivity Reaction

Hypersensitivity reactions may require immediate intensive care. Bintrafusp alfa should be administered in a setting that allows immediate access to an intensive care unit or equivalent environment and administration of therapy for anaphylaxis, such as the ability to implement immediate resuscitation measures. Potent steroids (e.g. dexamethasone), catecholamines (e.g. epinephrine), allergy medications (IV antihistamines), bronchodilators, or equivalents and oxygen should be available for immediate access.

A complete guideline for the emergency treatment of anaphylactic reactions according to the Working Group of the Resuscitation Council United Kingdom and can be found at <https://www.resus.org.uk/pages/reaction.pdf>.

#### Flu-Like Symptoms

Treatment is based on clinical assessment and at the discretion of the Investigator. For prophylaxis of flu like symptoms, a nonsteroidal anti-inflammatory drug (NSAID), e.g., ibuprofen 400 mg or comparable NSAID dose, may be administered 2 hours before and 8 hours after the start of each IV infusion.

#### Additional Modifications for Patients with Grade 2 Infusion-Related Reactions

If in the event of a Grade 2 infusion-related reaction that does not improve or worsens after implementation of the modifications indicated in Table 6 (including reducing the infusion rate by 50%), the Investigators may consider treatment with corticosteroids, and the infusion should not be resumed. At the next dose, the Investigators may consider the addition of H2 blocker antihistamines (e.g., famotidine or ranitidine), meperidine, or ibuprofen to the mandatory premedication. Prophylactic steroids are NOT permitted.

#### Severe Hypersensitivity Reactions

If hypersensitivity reaction occurs, the patient must be treated according to the best available medical practice. A complete guideline for the emergency treatment of anaphylactic reactions according to the Working Group of the Resuscitation Council (United Kingdom) can be found at <https://www.resus.org.uk/pages/reaction.pdf>. Patients should be instructed to report any delayed reactions to the Investigators immediately.

Symptoms include impaired airway, decreased oxygen saturation (<92%), confusion, lethargy, hypotension, pale or clammy skin, and cyanosis. These symptoms can be managed with epinephrine injection and dexamethasone. Patients should be placed on monitor immediately, and the intensive care unit (ICU) should be alerted for possible transfer if required.

#### 5.6.5 Management of Immune-Related Adverse Events (IrAEs)

Because inhibition of PD-L1 by anti-PD-L1 component stimulates the immune system, bintrafusp alfa may cause toxicity by increasing the immune response, leading to inflammatory reactions collectively referred to as immune-related adverse events (irAEs).

Immune-related AEs are specific to immunotherapies and vary by organ system. Following immune-related AEs are important identified risks for bintrafusp alfa:

- Immune-related pneumonitis
- Immune-related hepatitis

- Immune-related colitis
- Immune-related nephritis and renal dysfunction
- Immune-related endocrinopathies
- (thyroid disorders, adrenal insufficiency, type 1 diabetes mellitus, pituitary disorders)
- Immune related rash
- Other immune-related events (myositis, myocarditis, encephalitis)

Following immune-related AEs are important potential risks for bintralusp alfa:

- Guillain-Barré syndrome
- Uveitis
- Pancreatitis
- Myasthenia gravis/myasthenic syndrome

Recommended guidance and management for specific irAEs are provided in the current NCCN guideline available at <http://www.nccn.org>.

Requirements in addition to NCCN guidelines:

- Permanent treatment discontinuation is required in case of immune-related Grade 4 rash/inflammatory dermatitis, nephritis, autoimmune hemolytic anemia, hemolytic uremic syndrome, aplastic anemia, immune thrombocytopenia, acquired thrombotic thrombocytopenic purpura inflammatory arthritis, myositis and polymyalgia-like syndrome.
- For Grade 4 immune-related lymphopenia, permanent treatment discontinuation will be required, if lymphopenia is considered immune-related in nature, no clear alternative explanation exists for the event, and it does not resolve within 14 days. Permanent treatment discontinuation is not required when the AE is manifested by a single laboratory value out of normal range without any clinical correlates. In this case, treatment should be held until the etiology is determined. If the event is not considered immune-related and resolves to Grade  $\leq 1$ , restarting treatment may be considered.
- For Grade 1 immune-related pneumonitis: continue treatment. If clinically indicated, monitor participants weekly or more frequently as needed with history, physical examination and pulse oximetry. If symptoms appear and/or changes in the physical exam are noted, treat as Grade 2.
- For myositis: in case of management with rituximab, treatment should be discontinued.

The side effects listed below may be temporary, long term, permanent, life-threatening or result in death. However, most of these side effects are reversible.

#### **General Principle of Treatment of irAEs (NCI CTCAE grade):**

- Grades 1 to 2: treat symptomatically or with moderate dose steroids, more frequent monitoring.

- Grades 1 to 2 (persistent): manage similar to high grade AE (Grades 3 to 4).

Grades 3 to 4: treat with high dose corticosteroids or equivalent and/or other immunosuppressant as needed

### ***MANAGEMENT OF SKIN irAES IN PATIENTS TREATED WITH ICPis***

1.0 Skin Toxicities	
1.1 Rash/inflammatory dermatitis	

Definition: Erythema multiforme minor (a targetoid reaction in the skin and mucous membranes usually triggered by infections, such as herpes simplex viruses, but can be associated with an immune-related drug eruption and if progresses to erythema multiforme major, it can be a harbinger of SCAR, such as SJS), lichenoid (resembling the flat-topped, polygonal, and sometimes scaly or hypertrophic lesions of lichen-planus), eczematous (inflammatory dermatitis characterized by pruritic, erythematous, scaly, or crusted papules or plaques on the skin, which is vulnerable to superinfection, psoriasiform [resembling the well-demarcated, erythematous, and scaly papules and plaques of psoriasis], morbilliform [a nonpustular, nonbullous measles-like exanthematous rash of the skin often referred to as “maculopapular” and without systemic symptoms or laboratory abnormalities, excluding occasional isolated peripheral eosinophilia, palmoplantar erythrodysesthesia [hand-foot syndrome; redness, numbness, burning, itching, and superficial desquamation of the palms and soles], neutrophilic dermatoses [eg, Sweet syndrome], and others])
	
Diagnostic work-up	

Pertinent history and physical examination
 
Rule out any other etiology of the skin problem, such as an infection, an effect of another drug, or a skin condition linked to another systemic disease or unrelated primary skin disorder
 
If needed, a biologic checkup, including a blood cell count and liver and kidney tests
 
Directed serologic studies if an autoimmune condition is suspected, such as lupus or dermatomyositis: a screening antinuclear antibody test, SS-A/Anti-Ro, SS-B/Anti-La if predominantly photodistributed/photosensitivity, antihistone, double-stranded DNA, and other relevant serologies. Consider expanding serologic studies or diagnostic work-up if other autoimmune conditions are considered based on signs, symptoms Skin biopsy
 
Consider clinical monitoring with use of serial clinical photography
 
Review full list of patient medications to rule out other drug-induced cause for photosensitivity
	
Grading	Management
Grading according to CTCAE is a challenge for skin. Instead, severity may be based on BSA, tolerability, morbidity, and duration.	
G1: Symptoms do not affect the quality of life or controlled with topical regimen and/or oral antipruritic	
Continue ICPi
 
Treat with topical emollients and/or mild-moderate potency topical corticosteroids
 
Counsel patients to avoid skin irritants and sun exposure

G2: Inflammatory reaction that affects quality of life and requires intervention based on diagnosis	
Consider holding ICPi and monitor weekly for improvement. If not resolved, interrupt treatment until skin AE has reverted to Grade 1
 
Consider initiating prednisone (or equivalent) at dosing 1 mg/kg, tapering over at least 4 weeks
 
In addition, treat with topical emollients, oral antihistamines, and medium- to high-potency topical corticosteroids

G3: As G2 but with failure to respond to indicated interventions for a G 2 dermatitis	
Hold ICPi therapy and consult with dermatology to determine appropriateness of resuming
 
Treat with topical emollients, oral antihistamines, and high-potency topical corticosteroids
 
Initiate (methyl)prednisolone (or equivalent) 1-2 mg/kg, tapering over at least 4 weeks

G4: All severe rashes unmanageable with prior interventions and intolerable	
Permanently discontinue ICPi
 
Systemic corticosteroids: IV (methyl)prednisolone (or equivalent) dosed at 1-2 mg/kg with slow tapering when the toxicity resolves

1.0 Skin Toxicities	
	
Monitor closely for progression to severe cutaneous adverse reaction
 
Should admit patient immediately with direct oncology involvement and with an urgent consult by dermatology

1.2 Bullous dermatoses	

Definition: Including bullous pemphigoid or other autoimmune bullous dermatoses, bullous drug reaction
 
Diagnostic work-up
 
Physical examination
 
Rule out any other etiology of the skin problem, such as an infection, an effect of another drug, or a skin condition linked to another systemic disease
 
If needed, a biologic checkup, including a blood cell count, liver, and kidney tests; consider serum antibody tests to rule out bullous pemphigoid or, under the guidance of dermatology, sending patient serum for indirect immunofluorescent testing to rule out other autoimmune blistering diseases
 
Referral to dermatology for blisters that are not explained by infectious or transient other causes (eg, herpes simplex, herpes zoster, bullous impetigo, bullous insect bite, friction or pressure blister)
 
Consider skin biopsy (both hematoxylin and eosin evaluation of lesional skin and direct immunofluorescence evaluation of perilesional skin)
	
Grading	Management
G1: Asymptomatic, blisters covering < 10% BSA and no associated erythema	
If blisters are < 10% BSA, asymptomatic, and noninflammatory (such as the case with friction blisters or pressure blisters), cessation of ICPi is not necessary, and only observation and/or local wound care is warranted.
 
When symptomatic bullae or erosions, which are deroofed vesicles or bullae, are observed on the skin or mucosal surfaces, the cutaneous irAE is by definition considered at least G2
 
See G2 management recommendations


G2: Blistering that affects quality of life and requires intervention based on diagnosis not meeting criteria for Grade > 2
 
Blisters covering 10%-30% BSA
	
Hold ICPI therapy and consult with dermatology for work-up and to determine appropriateness of resuming
 
Attention given to general local wound care, which includes plain petrolatum ointment and bandages or plain petrolatum ointment gauze and bandage over any open erosions, which are left over on the skin after the blister has popped or if the roof of the blister easily sloughs off
 
Counsel patients to avoid skin irritants and overexposure to sun, wear protective clothing, use sunscreens
 
Work-up for autoimmune bullous disease as above
 
Initiate Class 1 high-potency topical corticosteroid (eg, clobetasol, betamethasone or equivalent) and reassess every 3 days for progression or improvement
 
Low threshold to initiate treatment with prednisone (or equivalent) at 0.5-1 mg/kg dosing and taper over at least 4 weeks
 
Monitor patients with G2 irAEs closely for progression to involvement of greater BSA and/or mucous membrane involvement. Consider following patients closely using serial photography
 
Primer on monitoring for complicated cutaneous adverse drug reactions:

--	---

1.0 Skin Toxicities	
	Review of systems: Skin pain (like a sunburn), fevers, malaise, myalgias, arthralgias, abdominal pain, ocular discomfort or photophobia, sores or discomfort in the nares, sores or discomfort in the oropharynx, odynophagia, hoarseness, dysuria, sores or discomfort in the vaginal area for women or involving the meatus of the penis for men, sores in the perianal area, or pain with bowel movements
	Physical examination: Include vital signs and a full skin examination specifically evaluating all skin surfaces and mucous membranes (eyes, nares, oropharynx, genitals, and perianal area). Assess for lymphadenopathy, facial or distal extremity swelling (may be signs of DIHS/DRESS). Assess for pustules or blisters or erosions in addition to areas of “dusky erythema,” which may feel painful to palpation. To assess for a positive Nikolsky sign, place a gloved finger tangentially over erythematous skin and apply friction parallel to the skin surface. Nikolsky sign is positive if this results in detached or sloughing epidermis demonstrating poor attachment of the epidermis to the dermis, which is the case in some autoimmune disorders (eg, pemphigus) and SJS/TEN
G3: Skin sloughing covering > 30% BSA with associated pain and limiting self-care ADL	Hold ICPI therapy and consult with dermatology to determine appropriateness of resuming Administer IV (methyl)prednisolone (or equivalent) 1-2 mg/kg, tapering over at least 4 weeks If bullous pemphigoid is diagnosed, it may be possible to avoid long-term use of systemic corticosteroids and treat with rituximab, as an alternative approach to treating the irAE Seek infectious disease consultation if patient might have secondary cellulitis or if patient has other infection risk factors, such as neutropenia, etc.

G4: Blisters covering > 30% BSA with associated fluid or electrolyte abnormalities	
Permanently discontinue ICPi
 
Admit patient immediately and place under supervision of a dermatologist
 
Administer IV (methyl)prednisolone (or equivalent) 1-2 mg/kg with tapering over at least 4 weeks when the toxicity resolves
 
If bullous pemphigoid is diagnosed, it may be possible to avoid long-term use of systemic corticosteroids and treat with rituximab as an alternative approach to treating the irAE
 
Seek infectious disease consultation if patient might have secondary cellulitis or if patient has other infection risk factors, such as neutropenia, etc

1.3 SCARs, including SJS, TEN, acute generalized exanthematous pustulosis, and DRESS/DIHS	
Definition: Severe changes in either structure or functions of skin, the appendages or the mucous membranes due to a drug	
Diagnostic work-up	Total body skin examination with attention to examining all mucous membranes as well as complete review of systems

1.0 Skin Toxicities	
Rule out any other etiology of the skin problem, such as an infection, an effect of another drug, or a skin condition linked to another systemic disease	
A biologic checkup, including a CBC with differential test, and liver and kidney function tests, including urinalysis, in addition to the blood work; if the patient is febrile, blood cultures should be considered as well	
Skin biopsies to assess for full-thickness epidermal necrosis, as is seen in SJS/TEN, as well as other possible etiologies like paraneoplastic pemphigus or other autoimmune blistering dermatoses or other drug reactions, such as acute generalized exanthematous pustulosis	
Consider following patients closely using serial clinical photography	
If mucous membrane involvement or blistering is observed on the skin, consider early admission to a burn center for further monitoring and management. Primer on monitoring for complicated cutaneous adverse drug reactions:	
Review of systems: Skin pain (like a sunburn), fevers, malaise, myalgias, arthralgias, abdominal pain, ocular discomfort or photophobia, sores or discomfort in the nares, sores or discomfort in the oropharynx, odynophagia, hoarseness, dysuria, sores or discomfort in the vaginal area for women or involving the meatus of the penis for men, sores in the perianal area, or pain with bowel movements	
Physical examination: Include vital signs and a full skin examination specifically evaluating all skin surfaces and mucous membranes (eyes, nares, oropharynx, genitals, and perianal area). Assess for lymphadenopathy, facial or distal extremity swelling (may be signs of DIHS/DRESS). Assess for pustules or blisters or erosions in addition to areas of “dusky erythema,” which may feel painful to palpation. To assess for a positive Nikolsky sign, place a gloved finger tangentially over erythematous skin and apply friction parallel to the skin surface. Nikolsky sign is positive if this results in detached or sloughing epidermis demonstrating poor attachment of the epidermis to the dermis, which is the case in some autoimmune disorders (eg, pemphigus) and SJS/TEN	
Grading	Management
All Grades	In cases of suspected SJS or any mucous membrane involvement, discontinue ICPi treatment and monitor closely for improvement, regardless of grade
G1: NA	For SCARs, there is no G1 category; if lower BSA is involved with bullae or erosions, there should remain a high concern that this reaction will progress to G3 or G4
G2: Morbilliform (“maculopapular”) exanthem covering 10%-30% BSA with systemic symptoms, lymphadenopathy, or facial swelling	Hold ICPi and monitor patients closely every 3 days with G2 irAEs for progression to involvement of greater BSA and/or mucous membrane involvement  Consider following patients closely using serial photography  Initiate therapy with topical emollients, oral antihistamines, and medium- to high-strength topical corticosteroids  Consider initiation of prednisone (or equivalent) 0.5-1 mg/kg tapered over at least 4 weeks

G3: Skin sloughing covering < 10% BSA with mucosal involvement associated signs (eg, erythema, purpura, epidermal detachment, mucous membrane detachment)	
Hold ICPI therapy and consult with dermatology
 
Treat skin with topical emollients and other petrolatum emollients, oral antihistamines, and high-strength topical corticosteroids; dimethicone may also be offered as an alternative to petrolatum
 
Administer IV (methyl)prednisolone (or equivalent) 0.5-1 mg/kg and convert to oral corticosteroids on response, wean over at least 4 weeks
 
Admit to burn and/or consult wound services with attention to supportive care, including fluid and electrolyte balance, minimizing insensible water losses, and preventing infection
 
Given the immune mechanism of action of these medicines, use of immune suppression is warranted and should be offered

---	---

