1.0 Skin Toxicities	
	For mucous membrane involvement of SJS or TEN, appropriate consulting services should be offered to guide management in preventing sequelae from scarring (eg, ophthalmology; ear, nose, and throat; urology; gynecology; etc, as appropriate)
G4: Skin erythema and blistering/sloughing covering ≥ 10% to > 30% BSA with associated signs (eg, erythema, purpura, epidermal detachment, mucous membrane detachment) and/or systemic symptoms and concerning associated blood work abnormalities (eg, liver function test elevations in the setting of DRESS/DIHS)	
Permanently discontinue ICPi
 
Admit patient immediately to a burn unit or ICU with consulted dermatology and wound care services
 
Consider further consultations based on management of mucosal surfaces (eg, ophthalmology; urology; gynecology; ear, nose, and throat surgery; etc) Initiate IV (methyl)prednisolone (or equivalent) 1-2 mg/kg, tapering when toxicity resolves to normal
 
IVIG or cyclosporine may also be considered in severe or corticosteroid-unresponsive cases
 
Consider pain/palliative consultation and/or admission in patients presenting with DRESS manifestations

Additional considerations: The usual prohibition of corticosteroids for SJS is not relevant here, as the underlying mechanism is a T-cell immunodirected toxicity
 
Adequate suppression is necessary with corticosteroids or other agents and may be prolonged in cases of DRESS/DIHS
 
All recommendations are expert consensus based, with benefits outweighing harms, and strength of recommendations are moderate
	

Abbreviations: ADL, activities of daily living; AE, adverse event; BSA, body surface area; CBC, complete blood count; CTCAE, Common Terminology Criteria for Adverse Events; DIHS, drug-induced hypersensitivity syndrome; DRESS, drug reaction with eosinophilia and systemic symptoms; G, Grade; ICPi, immune checkpoint inhibitor; ICU, intensive care unit; irAE, immune-related adverse event; IV, intravenous; IVIG, intravenous immunoglobulin; NA, not applicable; SCAR, severe cutaneous adverse reactions; SJS, Stevens-Johnson syndrome; TENS, toxic epidermal necrolysis.

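### A drug-caused blistering or sloughing event that fits both skin tables is hold-and-possibly-resume in one and permanent discontinuation in the other, and nothing says which governs

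*Protocol*

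**What the plan says.** All references are to the Protocol; the tables are in section 5.6.5.

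- **Scope of table 1.2, bullous dermatoses:** "Including bullous pemphigoid or other autoimmune bullous dermatoses, bullous drug reaction".
- **Scope of table 1.3:** the heading is an open list, "SCARs, including SJS, TEN, acute generalized exanthematous pustulosis, and DRESS/DIHS", and the definition is "Severe changes in either structure or functions of skin, the appendages or the mucous membranes due to a drug".
- **Table 1.2, Grade 2:** "Blisters covering 10%-30% BSA", or blistering that affects quality of life and needs intervention. Study drug is held and dermatology is consulted.
- **Table 1.2, Grade 3:** "G3: Skin sloughing covering > 30% BSA with associated pain and limiting self-care ADL". The action is "Hold ICPI therapy and consult with dermatology to determine appropriateness of resuming".
- **Table 1.2, Grade 4:** blisters over more than 30% BSA plus fluid or electrolyte abnormalities. Study drug is permanently discontinued and the patient admitted.
- **Table 1.3, Grade 4:** "G4: Skin erythema and blistering/sloughing covering ≥ 10% to > 30% BSA with associated signs" (epidermal detachment is one listed example) and/or systemic symptoms with concerning blood results. Study drug is permanently discontinued, with immediate admission to a burn unit or ICU.
- **Table 1.3, all grades:** suspected SJS or any mucous membrane involvement means discontinuing whatever the grade.
- **Section 5.6.2:** suspected immune-related events go to the irAE guidance.
- **Section 5.6.3:** Grade 3 adverse drug reactions require permanent discontinuation, apart from a short list of exceptions, none of which describes skin sloughing.

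**The concern.** The two tables are presented as separate categories, but their written definitions are not mutually exclusive. A severe blistering reaction caused by study drug is a bullous drug reaction, which is table 1.2, and it is also a severe skin change due to a drug, which is table 1.3. For that event the tables assign different grades, and the grade decides whether study drug may later be restarted and whether burn-unit or ICU admission is prescribed. Sections 5.6.2 and 5.6.3 do not settle the matter, because one sends the event to the tables and the other gives an instruction of its own.

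What is at stake is re-exposure to study drug after a severe skin event, in a protocol whose section 5.6.1 lists pemphigoid-type and other skin reactions among the identified risks.

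**Working it through.** No sample size, error rate or event count is involved, so the check is a comparison of rules for a defined patient.

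**Case A, the clearest overlap.** A drug-caused event with sloughing over more than 30% BSA, erythema, epidermal detachment, pain and limited self-care. There is no suspected SJS, no mucosal involvement and no fluid or electrolyte abnormality.

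| Source | Grade | Final action on study drug | Care setting stated |
|---|---|---|---|
| Table 1.2 | 3 (Grade 4 would need a fluid or electrolyte abnormality) | Hold; dermatology advises on resuming | Dermatology consult; no admission stated |
| Table 1.3 | 4 (above 10%, with erythema and an associated sign) | Permanently discontinue | Burn unit or ICU |
| Section 5.6.3, if the 1.2 grade is carried over | 3 | Permanently discontinue; no exception fits | None stated |

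The two tables are 4 − 3 = 1 grade apart. Sloughing is itself epidermal detachment, so the associated-sign condition in table 1.3 adds nothing to separate the two here. The erythema condition does have to be met.

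**Case B, 10–30% BSA.** Blisters alone are Grade 2 in table 1.2: hold. Table 1.3 reaches Grade 4 only if there is also erythema together with the associated signs and/or systemic symptoms with blood abnormalities. When those are present and the event is drug-caused, the tables are 4 − 2 = 2 grades apart. When they are absent, the event does not meet table 1.3 Grade 4 and there is no conflict at that grade.

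**Does any other text choose between the tables?**

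1. The all-grades row of table 1.3 covers only suspected SJS or mucosal involvement, both absent in Case A.
2. The requirements that section 5.6.5 adds to the NCCN guidance name Grade 4 rash/inflammatory dermatitis. They name neither bullous dermatoses nor severe cutaneous adverse reactions.
3. Section 5.6.2 points suspected immune-related events to the irAE guidance without saying which table, or whether that guidance displaces section 5.6.3.
4. Section 5.6.3 would discontinue in Case A, which agrees with table 1.3 and disagrees with the table 1.2 Grade 3 row.

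None of the four gives a precedence rule.

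**The table 1.3 Grade 4 bound.** A range running from at least 10% to more than 30% has a lower limit and no upper one. Read literally it means any extent of 10% or more. It leaves no gap, but it is not a range and should be rewritten.

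**The case against.** The strongest reply is that the tables are organised by diagnosis, and different diagnoses may properly carry different thresholds. The protocol supplies a work-up to separate them. Table 1.2 refers unexplained blisters to dermatology, considers biopsy, and carries a primer on complicated drug reactions that includes the Nikolsky sign. Table 1.3 uses biopsy to distinguish SJS/TEN from autoimmune blistering disease and other drug reactions. This stands for established diagnoses: bullous pemphigoid belongs in table 1.2 and no conflict arises. It does not dispose of the bullous drug reaction, which remains within both written definitions after work-up, nor of the period before a diagnosis is made.

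A reader might infer that the tables give opposite stopping rules at the bedside. The text does not support that. Both stop study drug at once, and both use the same intravenous steroid range (1–2 mg/kg) in Case A. Under table 1.2 any restart waits for dermatology. The difference is in the final action and the level of care.

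A reader might also compare table 1.3 Grade 3 (sloughing below 10%) with table 1.2 Grade 3 (above 30%). Those rows are not like for like: the 1.3 row requires mucosal involvement, table 1.2 already makes symptomatic mucosal bullae or erosions at least Grade 2, and all three rows say hold. The 10–30% comparison likewise holds only with the added conditions in Case B.

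Finally, it can be said that section 5.6.3 settles Case A, because the event is drug-caused and discontinuation follows whichever table is used. That would be persuasive if section 5.6.2 did not send suspected immune-related events to the tables, where the Grade 3 row leaves resumption open. As written, it adds a further inconsistency.

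**Conclusion.** The contradiction is real but narrow, and minor in weight. It applies to drug-caused blistering or sloughing that meets both definitions, or whose diagnosis is unsettled, without suspected SJS, mucosal involvement, or fluid or electrolyte abnormality. Within that group, more than 30% sloughing may be followed by resumption under table 1.2 but not under table 1.3 or section 5.6.3.

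The conclusion assumes that the definitions are applied as written, that erythema is present, and, for section 5.6.3, that the table grade carries over. That section does not name its grading scale, while section 6.1 grades all adverse events by CTCAE v4.0.

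The number of patients affected cannot be estimated. The one related case reported in the background, a skin infection secondary to localized bullous pemphigoid among 19 first-in-human patients, is autoimmune disease and falls under table 1.2, so it gives no rate for the overlap.

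A reader might infer that the trial's tolerability result would be distorted. The protocol does not support that. Section 6.2 grades safety outcomes by CTCAE v4 and defines no discontinuation-rate endpoint, and the stopping rule in section 7.3 counts treatment-related serious adverse events, whose seriousness section 6.6.2 has assessed independently of severity.

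**What to change.** In a protocol amendment:

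1. Reconcile the table 1.2 Grade 2 and Grade 3 rows, the table 1.3 Grade 4 row, and sections 5.6.2 and 5.6.3 on final action on study drug and level of care.
2. Add one sentence saying which governs when an event meets both definitions or the diagnosis is not yet settled.
3. Rewrite the table 1.3 Grade 4 BSA bound so that its limits are explicit.
4. Say whether the irAE tables or section 5.6.3 take precedence for immune-related adverse drug reactions, and which grading scale section 5.6.3 uses.

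The investigators choose the rule; none is proposed here. The cost is a few sentences of text, with no effect on sample size, endpoints or analysis.
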